# Clinical Investigation Plan (CIP)

Study Name: VivaSight-DL study (CIS-009)  
Ethical committee number: S-20180081

CLI-000427

Rev. 02

# Clinical Investigation Plan (CIP)

Study Name: VivaSight-DL study (CIS-009)  
 Ethical committee number: S-20180081

CLI-000427

Rev. 02

## 1. INTRODUCTION

Single-lung ventilation refers to the mechanical separation of ventilation between the two lungs, resulting in ventilation of only one lung. This technique is used either to facilitate exposure of the surgical field or to anatomically isolate one lung from a pathologic process of the other lung. The two most common methods of single-lung ventilation for thoracic surgery are utilisation of a Double-Lumen Tube (DLT) or a single-lumen endotracheal tube with a bronchial blocker (1).

Single-lung ventilation is required in several clinical situations and for various surgical procedures. Perhaps the most frequent indication is thoracic surgery during which single-lung ventilation and collapse of the operated lung facilitate the operation. DLTs are the most common approach to single-lung ventilation. The DLT consists of a proximal tracheal end and a distal bronchial end, reaching into either the left or right side of the lung (2).

However, DLTs are difficult to insert and they often move during surgical lung manipulation or when changing the position of the patient which can compromise the patient safety and cause life-threatening complications for the patient (2). In order to avoid that and secure a more proper placement of the tube VivaSight-DL have been introduced. VivaSight-DL has an integrated camera allowing continuous visualization of its position in the trachea. Furthermore, the VivaSight-DL is the world's only fully disposable tube with an integrated imaging system and ventilation for accurate placement and consistent, real-time airway control. Lastly, as VivaSight-DL is a single-use device it prevents contamination of the ventilated lung (3,4).

The CIP was made according to the Council Directive 93/42 EEC of 14 June 1993 and amendment 2007/47/EC (5), the guidelines set out in ISO 14155 (6), ISO 14971 (7) and the Helsinki Declaration (8).

## 2. AIM OF THE INVESTIGATION

The aim of this study is to make a health economic evaluation comparing novice physicians use of VivaSight-DL and a conventional DLT for single-lung ventilation during thoracic surgery. To do so, clinical outcomes that influence the cost of the procedures, including the incidence of fibreoptic bronchoscope (FOB) use, time and need of tube repositioning (see section 4), will be assessed and analysed.

## 3. HYPOTHESIS

Is VivaSight-DL more cost-effective than a conventional DLT?

$H_0$ : VivaSight-DL is not more cost-effective than a conventional DLT because the incidence of FOB use is not lower for Vivasight-DL

$H_A$ : VivaSight-DL is more cost-effective than a conventional DLT because the incidence of FOB use is significantly lower for VivaSight-DL resulting in workflow optimization.

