## 5. DESIGN OF INVESTIGATION

### 5.1 Design of investigation

A randomized, controlled single-centre investigation comparing the VivaSight-DL and the conventional DLT at a teaching hospital. A pilot study including up to 10 subjects will be performed prior to the investigation is initiated (see section 7.1). The investigation will include a total of 50 adult subjects (25 subjects in each group) admitted to department V at OÜH with established indication of single lung ventilation.

The objective of the investigation is to compare the number of times the tube position needs to be verified with a scope and relevant costs between VivaSight-DL and conventional DLT in a cost-effectiveness analysis. Furthermore, procedure time, intubation attempts and repositioning will be assessed (see section 4. End Points).

The study will start to recruit subjects within four weeks after Ethical Committees approval and nine months ahead or until 50 subjects have been recruited. If the number of subjects cannot be included in time, the sponsor and Principal Investigator will decide if the study should be closed.

Each subject enrolled in the investigation can only participate in the investigation once. The study duration for each subject is counting from the indication of the need of a single lung ventilation procedure until the subject has completed the questionnaire. Only one test device should be used per subjects (VivaSight-DL or conventional DLT).

Only subjects who can be clinically evaluated as eligible for a single lung ventilation procedure i.e. complies with the listed inclusion and exclusion criteria may be included in the investigation. If subjects or their legal representatives do not consent to the investigation or if the subject is not assigned a novice physician to perform the procedure, the procedure will be performed regardless – however off this investigation. A Case Report Form (CRF, appendix III) must be filled in for each subject that is assigned a novice physician to perform the intubation and has signed the Informed Consent (appendix II), and therefore is included in the investigation. After the surgery the subjects will be asked to answer a questionnaire regarding health-related life quality and side effects from the procedure (appendix IV). If the subject cannot give feedback, the reason is stated in the questionnaire.

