## 7.10 Collection of cost data

To enable an exact cost-model of single-lung ventilation, it is necessary to fully understand all processes related to the procedure. A research assistant will map all processes related to the procedure at the investigational site. Based on this, the research assistance collects all costs related to single-lung ventilation.

Resources and personnel time used for the individual processes will be tracked on a worksheet based on the initial mapping of the processes related to single-lung ventilation. This includes but is not excluded to personnel cost, procedure times, utilities, single-use equipment and capital equipment used during single-lung ventilation. Furthermore, all resources and times related to bronchoscopes will be collected via following at least 5 bronchoscopes from storage/drying cabinets through procedure, cleaning, reprocessing and back to storage/drying cabinets.

The following cost data will be collected via the investigational sites own records: Capital cost, repair costs, maintenance cost, cost of service agreements, cleaning verification costs, audit costs, personnel costs, cost of single-use equipment, administrative costs, cost of utilities and detergents. Note that if additional related costs are detected during the study they will be included in the cost-model.

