## 18. DATA MANAGEMENT AND STATISTICAL ANALYSIS

### 18.1 Sample size

The following formula is used to validate that the chosen sample size is sufficient to detect an effect on the primary outcome):

$$n_1 \geq \left( \frac{(\sigma_{DLT}^2 + \sigma_{vivasight}^2) * (\lambda_z + \lambda_\beta)^2}{(\bar{x}_{DLT} - \bar{x}_{Vivasight})^2} \right)$$

Combined standard deviation and grand mean are based on three studies (2,12,13).

$$\begin{aligned} \bar{x}_{DLT} &= 0,37234 \text{ bronchoscopes used to correct DLT placement} \\ \bar{x}_{vivasight} &= 0,01087 \text{ bronchoscopes used to correct vDLT placement} \\ \sigma_{DLT}^2 &= 0,23622 \text{ bronchoscopes} \\ \sigma_{vivasight}^2 &= 0,01087 \text{ bronchoscopes} \end{aligned}$$

We set power to 90% thus the  $\lambda_\beta = 1.28$  and significance level at 5%  $\rightarrow \frac{0.05}{2} = 0,025 \rightarrow \lambda_z = 1,96$

Thereby, to reject the  $H_0$  the sample size must be:

$$\begin{aligned} n_1 &\geq \left( \frac{(0,23622 + 0,01087) * (1,96 + 1,28)^2}{(0,37234 - 0,01087)^2} \right) = 19,852 \text{ patients} \\ N &= 19,852 * 2 = 39,7035 \rightarrow 40 \text{ patients} \end{aligned}$$

Therefore, a total sample size (N) of 40 generates a power of 90%. A sample size of 50 patients allows a potential dropout rate of 20 percent.

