## 18.3.3 Method of statistical analysis in relation to objectives

### Primary outcome:

- Number of times where fiberoptic confirmation of tube position during intubation or surgery is needed

If the observations are normally distributed, a student t-test will be used to examine if number of times the tube position needs to be verified with a bronchoscope is significantly different for procedures using VivaSight-DLT compared to a conventional DLT. If the observations are not normally distributed, a Mann-Whitney U test will be used.

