### 18.3.4 Level of significance and handling of multiplicity

All statistical tests will be two-sided and will be performed at the significance level ( $\alpha$ ) of 5%. To account for the explorative analysis', a Bonferroni correction is used.

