## 18.7 Health economic evaluation

The cost of all relevant processes related to single-lung ventilation will be summed and the average cost per procedure will create the cost input into a cost-effectiveness model. Capital costs will be discounted at the national appropriate discount rate of 4.05 and depreciated over the assumed life span of the device (14).

The effects measures included in the cost-effectiveness model includes:

- The primary outcome: the risk of needing a bronchoscope to check DLT placement
- The subsequent risk of cross-infection due to bronchoscopy. This risk is calculated based on current evidence from the literature

Cost-effectiveness data will be analyzed as a base-case result via a decision tree running over a short time period of one year within the hospital setting where the procedure is taking place. This will result in the deterministic ICER.

The cost data, risks and base-case will be presented in a table.

To challenge the base-case robustness several 1-way deterministic sensitivity analyses will be conducted. Doing so, major contributors to the base-case result will be varied to test their contribution to the base-case. The one-way sensitivity results will be presented as a tornado plot. To validate the overall robustness and second order uncertainty of the base-case a probabilistic sensitivity analysis will be conducted. Here, all the stochastic variables contributing to the ICER will be varied simultaneously. The probabilistic sensitivity analysis will be presented in a cost-effectiveness plane.

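### The hypotheses are worded as cost-effectiveness conclusions, but the sample size and primary test address only bronchoscope use, and no rule links the economic results to them

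*Combined protocol and SAP*

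**What the plan says.** Section 2 sets an economic aim: "The aim of this study is to make a health economic evaluation comparing novice physicians use of VivaSight-DL and a conventional DLT". Section 3 asks whether VivaSight-DL is more cost-effective and gives two hypotheses in those terms. The alternative is "VivaSight-DL is more cost-effective than a conventional DLT because the incidence of FOB use is significantly lower for VivaSight-DL resulting in workflow optimization". The null denies cost-effectiveness, on the ground that FOB use is not lower.

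The confirmatory part of the plan concerns FOB use. The primary endpoint in section 4 is a count of fibreoptic confirmations during intubation or surgery. Section 18.1 opens with "The following formula is used to validate that the chosen sample size is sufficient to detect an effect on the primary outcome" and presents its result as the size needed to reject the null. Under section 18.3.3, "a student t-test will be used to examine if number of times the tube position needs to be verified with a bronchoscope" differs between devices, with a Mann-Whitney U test if the data are not normal. Section 18.3.4 adds "All statistical tests will be two-sided and will be performed at the significance level" of 5%.

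Costs appear elsewhere. Section 5.1 speaks of comparing verification with "a scope and relevant costs between VivaSight-DL and conventional DLT in a cost-effectiveness analysis". Section 7.10 says "Based on this, the research assistance collects all costs related to single-lung ventilation". Section 18.7 feeds average cost per procedure into a decision tree, reports an ICER, and adds one-way and probabilistic sensitivity analyses. Its effect measures are a literature-based cross-infection risk and "The primary outcome: the risk of needing a bronchoscope to check DLT placement".

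**The concern.** A hypothesis test supports only conclusions about the quantity it tests. Here that quantity is FOB use, while the statement to be rejected is that the device is not more cost-effective. Tube, monitor, personnel and reprocessing costs all bear on that statement, and none of them is in the test.

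As worded, a significant FOB result could be reported as establishing cost-effectiveness, whatever section 18.7 shows. Because the trial's aim is economic, this is its headline conclusion.

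There is a second, smaller mismatch. The economic model names the primary outcome as its effect but describes it as a risk, whereas sections 4, 18.3.3 and 18.5 make it an integer count. If some patients need the FOB more than once, the trial's primary effect and the model's effect are different quantities.

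**Working it through.** **1. The plan's own figure.** Inputs from section 18.1: means 0.37234 (conventional DLT) and 0.01087 (VivaSight-DL), variances 0.23622 and 0.01087, multipliers 1.96 and 1.28.

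- Difference: 0.37234 − 0.01087 = 0.36147.
- Variance sum: 0.23622 + 0.01087 = 0.24709.
- n per group = 0.24709 × (1.96 + 1.28)² / 0.36147² = 19.85, so 39.70 in total, rounded to 40.
- Allowing 20% dropout: 40 / 0.80 = 50.
- Power = Φ(0.36147 / √(0.24709/n) − 1.96), which is 90.2% at n = 20 per group and 95.3% at n = 25.

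The stated sizes reproduce. Every term is FOB use; no cost, price or net-benefit quantity appears.

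**2. What the two hypotheses cover.** Crossing the FOB result with the economic result:

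| FOB use | Economic result | Fits |
|---|---|---|
| lower | favourable | alternative |
| lower | unfavourable | neither |
| not lower | unfavourable | null |
| not lower | favourable | neither |

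The second row matters most. The FOB test would reject the null there, yet the alternative would be false.

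**3. Is there a linking rule elsewhere?** Section 18.7 names no willingness-to-pay threshold and no required probability of cost-effectiveness, and does not mention the hypotheses. Section 18.5 is headed as pass/fail criteria, but its entries for the outcomes are data-validity checks (integers, positive times). Neither section supplies the link.

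**4. How far the FOB test can inform cost.** The documents give no prices. As an assumption, let r be the extra VivaSight-DL cost per procedure divided by the cost of one FOB use, and ignore all other costs. Then incremental cost per procedure, in units of one FOB use, is r − 0.36147 at the planning difference:

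| r | Incremental cost |
|---|---|
| 0.10 | −0.26 |
| 0.25 | −0.11 |
| 0.36 | about 0 |
| 0.50 | +0.14 |
| 1.00 | +0.64 |

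Because r is not in the test statistic, the rejection rate is the same on every row. A simulation with 0/1 FOB use at the planning rates and 25 per group gave 97.7% at each of these premiums. The sign changes at r = 0.361. This illustrates cost-neutrality, not cost-effectiveness.

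**5. Count or risk.** Mean count = risk of any use + mean uses beyond the first, so the scales agree only if nobody has a repeat use.

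- For the control tube, section 7.5.2 (steps 11–15) writes the FOB into intubation, and section 7.6 writes it in again after lateral positioning. Both uses are recorded.
- If these uses count towards the endpoint, control any-use is near 100% and the control mean count is near 2. The scales then differ by design.
- The section 18.1 inputs do not describe that situation. They are labelled as bronchoscopes used to correct placement. They match 0/1 data numerically: 35/94 = 0.37234 with sample variance 0.23622, and 1/92 = 0.01087 with sample variance 0.01087. A count that never exceeded 1 would look the same.

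**The case against.** The strongest reply is that the plan does connect the two parts. Section 5.1 places FOB use and costs in one cost-effectiveness analysis, and section 18.7 takes the primary outcome as an effect measure. The reason clauses in section 3 can be read as naming FOB use as the operational criterion. Section 18.7 also commits to a table of costs and base case, a tornado plot and a cost-effectiveness plane, so an unfavourable economic result would be visible.

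Much of this stands. A reader might infer that the plan has no economic analysis, or one unconnected with the primary outcome; the documents show otherwise. Only a decision rule is missing. Reading FOB use as a proxy does not supply one, because lower FOB use alone cannot establish cost-effectiveness when other costs enter section 18.7 and not the test.

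A reader might also object that a directional null is paired with two-sided tests. That adds little: testing a directional research hypothesis two-sided and then reading the direction is common practice. A significant excess of FOB use would simply not support the alternative.

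**Conclusion.** The point holds. The hypotheses claim more than the test that decides them can show, and nothing in sections 18.5 or 18.7 closes the gap. The sample-size arithmetic is correct for FOB use at the stated inputs and is not in dispute.

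The size of the problem cannot be put as an error rate. A reader might want a probability that the null is rejected while the device is not cost-effective. The documents do not support one: they give no prices, cost variance or threshold. A dearer device can still be cost-effective at a positive ICER, and cross-infection is a further effect. The 0.361 break-even rests on the planning difference and on FOB costs alone. It would move if the control group's routine uses count.

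The scale mismatch is secondary and conditional. It disappears if no patient has a repeat use. It is built in if the FOB uses written into the control procedure count, and the plan does not settle that.

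**What to change.** 1. In section 3, restate the hypotheses: the number of FOB uses per patient does not differ (null) or differs (alternative) between VivaSight-DL and the conventional DLT, two-sided as in section 18.3.4. Fix one wording in advance. It should not depend on which test is used, because section 18.3.3 chooses between the t-test and Mann-Whitney from the data.
2. State that a significant FOB result is a conclusion on FOB use only. Any cost-effectiveness conclusion rests on the section 18.7 incremental cost, ICER and probabilistic analysis, reported as estimation unless a threshold and rule are pre-specified.
3. In section 18.7, either use the mean FOB count as the model effect so that it matches the primary endpoint, or label any-use as a separate derived measure and carry repeat uses in the costs and the cross-infection exposure. Say there whether the routine control uses count.

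Items 1 and 2 are wording; the test, sample size and data collection do not change. Item 3 needs a small model change: a repeat-use branch or a cost term. The case report form (Appendix V) already records FOB counts for intubation and for surgery, and section 7.10 already collects the costs.

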## 4. END POINTS

### Primary end-point:

- Number of times where fiberoptic confirmation of tube position during intubation or surgery is needed

### Secondary end-points:

- Intubation time (seconds)
  - Time starts: when introducing the laryngoscope blade into the subject's mouth.
  - Time stops: when correct bronchial cuff placement is confirmed by capnography

# Clinical Investigation Plan (CIP)

Study Name: VivaSight-DL study (CIS-009)  
Ethical committee number: S-20180081

CLI-000427

Rev. 02

- Number of intubation attempts
  - Intubation attempt is defined as the number of intubation attempts until successful intubation is accomplished. If the endotracheal tube is incorrectly placed and the tube is withdrawn from the subjects throat it counts as one attempt.
  - If more than three intubation attempts are used the intubation is defined as a failure and the subject is excluded from the study.
- Number of times incorrect placement of the tube is prevented during intubation
  - Prevention of repositioning is a corrective action that ensures optimal ventilation of the subject without having to move the tube after the bronchial cuff is inflated. An example of a corrective action during intubation could be change of the tube direction if it starts to enter the right main bronchi instead of the left main bronchi when advanced down the throat.
- Number of times the tube needs to be repositioned during intubation
  - In this study, repositioning is defined as the action where the bronchial cuff needs to be deflated to move the tube into the right position.
- Number of times where the physician prevents repositioning of the tube during surgery
  - Prevention of repositioning is a corrective action that ensures optimal ventilation of the subject without having to move the tube after the bronchial cuff is inflated. An example of a corrective action during surgery could be optimization of the cuff sealing by deflating and inflating the cuff without moving the tube.
- Number of times the tube needs to be repositioned during surgery.
  - In this study, repositioning is defined as the action where the bronchial cuff needs to be deflated to move the tube into the right position.
- Repositioning time (seconds) during surgery
  - In this study, repositioning is defined as the action where the bronchial cuff needs to be deflated to move the tube into the right position.
  - Time starts: when the syringe is attached to the valve to deflate the bronchial cuff
  - Time stops: when correct bronchial cuff placement is verified by capnography
- Rate of restriction on the surgical procedure during repositioning of the tube
  - One of the following statements is chosen:
    - Not restricted
      - The surgical procedure is not restricted at all, the surgeon continues to work full speed
    - Restricted
      - The surgical procedure continues but with limited speed, the surgeon's ability to perform the procedures is affected.
    - Completely restricted
      - The surgical procedure is completely restricted (surgical procedure is paused), the surgeon is not able to work at all.
- Number of times the backup anesthesiologist is called into the operating room for assistance
- Time the back-up anesthesiologist spends on the procedure
  - Time starts: when the backup anesthesiologist answers the phone
  - Time stops: when the backup anesthesiologist leaves the operating room

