## 5.4 Randomisation

One randomization list will be prepared containing 50 participants. The randomization list is dividing equally the number of participants for the VivaSight-DL group and the conventional reusable DLT group (standard care at the respective centre).

The randomisation list will be created by using the website random.org (<https://www.random.org/lists/>) and repeating the randomization three times. The treatment will be named 1 (=VivaSight-DL), 2 (=conventional DLT) in the list.

Sponsor will prepare envelopes according to the randomisation list. All envelopes will be clearly numbered in succession and the number will act as the subject number in the investigation. The Investigator will draw an envelope in successive order after the informed consent is obtained from the subject and a physician with experience in < 50 DLT placements in patients is assigned for the procedure. If additional subjects are to be included, the number of subjects must correspond to at least one block. Ambu will supply the additional envelopes.

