## 6.5 Exclusion during the examination

The subject can be excluded during the investigation if:

- The subject or legal representative decides to abort the study
- The subject is assigned to a physician with experience in > 50 DLT intubations in patients
- The investigator considers it necessary to change the type of endotracheal tube used for the procedure
- The investigator assess that it is necessary to exclude the subject from the investigation to ensure safety of the subject

If a subject withdraw from the study before the study randomization envelopes seal is broken (example no. 10), then the next subject will continue with consecutive subject number (no. 11).

If the subject is excluded *after* the procedure is started, he or she will be treated and receive routine treatment. Reason for exclusion will be stated in the CRF but otherwise data will not be collected in the CRF.

If the subject is excluded *before* the procedure is started, he or she will receive routine treatment. Reasons for exclusion will be stated in the CRF but otherwise data will not be collected in the CRF.

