# Clinical Investigation Plan (CIP)

Study Name: VivaSight-DL study (CIS-009)  
 Ethical committee number: S-20180081

CLI-000427

Rev. 02

The investigation procedure will contain the following sections:

1. Recruitment of subjects
2. Preparation of procedure
3. Induction of anaesthesia
4. Intubation
5. Surgery
6. Subject monitoring during the surgery
7. Awakening of subject and follow up
8. Collection of cost data

Before the investigation is initiated all investigators will be instructed in the study protocol. Subjects will be recruited, and Informed Consent will be obtained by Investigators (nurses or physicians with at least two years of experience in anesthesia). The data will be collected on a CRF (paper or electronic format) during the procedure, when the CRF is completed the principal investigator will check that it is filled out correctly and sign it. Prior to the investigation a pilot will be run to test the data collection method in practice and ensure that the involved parts are familiar with the protocol (see section 7.1).

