## 7.3 Preparation of the procedure

Latest on the day of the procedure, the subject will be assigned a physician who will perform the intubation. If the subject is assigned a physician with experience in > 50 DLT intubations in patients, the subject will be excluded from the study and receive the standard treatment. If the subject is assigned a physician with experience in < 50 DLT intubations, the subject will be randomized to receive single-lung ventilation using either VivaSight-DL (test group) or Shiley™ Endobronchial Tube (control group).

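### Failed intubations, and possibly tube changes, are excluded after randomisation, and no analysis set by allocated arm is defined

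*Combined protocol and SAP*

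**What the plan says.** **Order of events.** Section 5.4: "The Investigator will draw an envelope in successive order after the informed consent is obtained from the subject", once a novice physician has been assigned. Section 7.3 places allocation in the preparation phase. Both come before intubation starts.

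**Losses after that point.**
- Section 4, under the attempts endpoint: "If more than three intubation attempts are used the intubation is defined as a failure and the subject is excluded from the study". This is not discretionary.
- Section 6.5 lists, among the grounds on which a subject can be excluded: "The investigator considers it necessary to change the type of endotracheal tube used for the procedure". For exclusions once the procedure has begun: "Reason for exclusion will be stated in the CRF but otherwise data will not be collected in the CRF".
- Section 18.3.2 leaves subjects who were intubated but not operated on out of the primary analysis, although the primary endpoint in section 4 counts bronchoscope confirmations in both phases. Dropouts before intubation leave every analysis.

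**Attempts endpoint.** Section 4: "Intubation attempt is defined as the number of intubation attempts until successful intubation is accomplished".

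**Withdrawals.** Section 6.4 stores data recorded before withdrawal but does not analyse them, and replaces the subject so that 50 are analysed. Section 18.3.2 uses dropouts' data up to the time of dropout. Section 18.1 presents 50 as already allowing for 20% dropout.

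**Who is analysed.** The only general rule is in section 18.5, which requires analysed patients to meet the eligibility criteria. No set is defined by allocated arm.

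**The concern.** Randomisation makes the arms comparable at the moment the envelope is opened. Needing more than three attempts, or having to change tube, happens later and may be caused by the tube. Removing those subjects compares the two devices among the cases in which each one worked. The sample-size allowance for dropout protects precision. It does not protect against loss that is related to the outcome.

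The estimate matters more here than the p-value. Section 2: "The aim of this study is to make a health economic evaluation". Section 18.7 takes the risk of needing a bronchoscope as an effect measure in the cost-effectiveness model, so a distorted risk difference goes straight into the ICER. Failed cases are also likely to be resource-intensive, and with data collection stopped their costs are incompletely captured.

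The attempts endpoint is affected by its own definition. It counts attempts up to success, and the subjects in whom success was not reached within the limit are taken out.

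**Working it through.** **1. The plan's own figure.** Section 18.1 inputs: means 0.37234 and 0.01087, variances 0.23622 and 0.01087, multipliers 1.96 and 1.28.

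n per arm = (0.23622 + 0.01087) × (1.96 + 1.28)² / (0.37234 − 0.01087)² = 19.852, so N = 39.70, rounded up to 40. Then 40 / 0.8 = 50. The sample size reproduces and is not in dispute. The means equal 35/94 and 1/92, so they behave as proportions of subjects.

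**2. Assumptions for the illustration.** The documents give no failure or tube-change rate. I take 25 per arm (section 5.1), k = 0 to 2 failures in an arm, and r = 1 if a failed case needed a bronchoscope, 0 if not. With m the risk among the rest:

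risk in arm = ((25 − k) × m + k × r) / 25

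**3. Section 18.1 scale (bronchoscope used to correct placement).** With failures excluded the difference is 0.3723 − 0.0109 = 0.361.

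| Failures kept (r = 1) | Risk difference | Change |
|---|---|---|
| 1 VivaSight-DL | 0.3723 − 0.0504 = 0.322 | −11% |
| 2 VivaSight-DL | 0.3723 − 0.0900 = 0.282 | −22% |
| 1 control | 0.3974 − 0.0109 = 0.387 | +7% |
| 2 control | 0.4226 − 0.0109 = 0.412 | +14% |
| 1 in each arm | 0.3974 − 0.0504 = 0.347 | −4% |

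Over all combinations of k and r the range is 0.25 to 0.41.

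**4. Cost-model scale (bronchoscope used to check placement).** Section 18.7 uses this measure. Sections 7.5.2 and 7.6 prescribe a bronchoscope for every control, at intubation and again after lateral positioning, so the control risk is 1. I keep 0.0109 for VivaSight-DL. With failures excluded: 1 − 0.0109 = 0.989. At fixed incremental cost, cost per bronchoscopy avoided changes by 0.989 / (new difference) − 1:
- one VivaSight-DL failure: 0.9891 / 0.9496 − 1 = +4.2%
- two VivaSight-DL failures: 0.9891 / 0.9100 − 1 = +8.7%
- extreme case, two failures per arm, with a bronchoscope needed only in the VivaSight-DL failures: 0.92 − 0.09 = 0.83, giving +19%

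The range of the difference on this scale is 0.83 to 0.99.

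**5. Primary test on that scale.** Take all controls at 2 uses, 23 VivaSight-DL subjects at 0 and two VivaSight-DL failures ranked above everyone. Then U = 2 × 25 = 50, against 312.5 expected. The tie-corrected SD is 45.46, z = (312.5 − 50 − 0.5) / 45.46 = 5.76, and p is about 8 × 10⁻⁹.

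**6. Attempts endpoint.** If k failures in one arm are ranked worst and everyone else needs one attempt, the Mann-Whitney probability is 0.5 + 0.5 × k/25. For k = 1, 2, 3 this is 0.52, 0.54, 0.56, with p = 0.34, 0.16, 0.08. Under the present rules these subjects contribute nothing.

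**The case against.** The strongest reply is that no failure rate is given, anticipated difficult airways are excluded (section 6.2) and physicians train on manikins first (section 6.3), so failures may be rare. That is fair, and it is why the figures above are illustrations only. It does not justify removing whatever failures occur.

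A reader might also infer more than the documents support:

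- **That the primary result is in danger.** On the section 18.1 inputs, ranking failures above every count takes simulated Mann-Whitney power from 98% to 85% with one VivaSight-DL failure and 55% with two. This depends on that scale, on failures in one arm only, and on the scoring: with two failures each scored as one bronchoscope use, power is about 70%; scored as 0, about 98%. With the prescribed control uses counted, the test is not at stake.
- **That the bias favours VivaSight-DL.** Control failures move the estimate the other way. The direction is unknown.
- **That nothing is known after exclusion.** Section 6.5 restricts the CRF only; section 13.2 still requires adverse events to be reported. Section 7 says "The data will be collected on a CRF (paper or electronic format) during the procedure", so entries made before exclusion may exist. The plan does not settle whether they are used.
- **That failed cases have no attempt count.** Sections 7.5.1 and 7.5.2 require attempts to be recorded. The gap is in the endpoint definition and the exclusion.
- **That section 18.5 removes failures as ineligible.** Section 6.4 has eligibility checked at inclusion, before the envelope, and section 18.5 can be read as referring to that check.
- **That sections 6.4, 6.5 and 18.3.2 conflict throughout.** They address withdrawal, exclusion and dropout. The conflict is clear only for subjects who withdraw.

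**Conclusion.** The plan is wrong as written on this point. It requires exclusion of failed intubations after allocation, permits exclusion on a tube change with CRF collection stopped, and drops subjects with an observed intubation-phase count from the primary analysis, with no analysis set by allocated arm. At risk are the effect estimate, the attempts result and the cost inputs. The significance of the primary test is not at risk if the bronchoscope uses prescribed for controls are counted.

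Size and direction cannot be determined from the documents. Under the assumptions stated, one or two VivaSight-DL failures needing a bronchoscope change the risk difference by −11% or −22% on the section 18.1 inputs, and cost per bronchoscopy avoided by about +4% or +9% on the cost-model scale. The cost figures hold incremental cost fixed, which is a simplification because a failed case may use a second tube. The change belongs before recruitment, since data not collected cannot be recovered at analysis.

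**What to change.** 1. **Analysis set (section 18.3).** Define the primary set as all randomised subjects in whom intubation was started, analysed in the allocated arm. Report dropouts before intubation by arm.
2. **Data collection (sections 4, 6.4, 6.5, 18.3.2).** State that a failed intubation or tube change does not end study data collection, leaving clinical management as the plan has it. Reconcile the three sections on exclusion, withdrawal and dropout so that data recorded up to withdrawal are used, subject to consent.
3. **Primary endpoint.** Count all bronchoscope uses in the allocated arm, and report uses with the allocated tube and uses after a switch separately. Give a worst-rank analysis of failures as a sensitivity analysis only.
4. **Intubated but not operated on.** Include these subjects with their observed count. Add a sensitivity analysis without them, because their observation period is shorter.
5. **Attempts endpoint (sections 4 and 18.3.3).** Keep failures as the worst category, use a rank test, and report failures and switches by arm.
6. **Replacement (sections 6.4 and 18.1).** Do not replace subjects once the envelope is opened, and reconcile replacement to 50 analysed with the 20% allowance (50 × 0.8 = 40, the number required).

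**Cost.** Wording changes and a few more CRF entries per failed case. The planned sample size does not change. Fewer than 50 may be analysed, and the estimates may become less favourable to either device. Counting uses after a switch is a choice of estimand, which is why item 3 asks for the two counts separately.
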